9.2 Data Analysis

9.2.1 General Considerations

Data will be collected and curated in a REDCap database [?] with support from the Human Subjects Core and exported into a suitable analysis format (e.g. STATA, SPSS, R analysis) for analysis. For continuous variables that are normally distributed we will summarize them using mean with standard derivations and for those that are non-normally distributed, we will summarize with medians and inter-quartile ranges. For dichotomous data we will provide proportions. In addition to the baseline and outcome data, we will also summarize the recruitment numbers, those participants lost to follow-up, protocol violations and other relevant data.

9.2.2 Study Participant Populations

As described above, the per protocol sample will consist of all active treatment participants completing DBPCFC3.

9.2.3 Study Participant Baseline Characteristics and Demographics

Summary of descriptive statistics for baseline and demographic characteristics will be provided for all enrolled participants. Demographic data will include age, race, sex, body weight, and height; these data will be presented in the following manner: summary tables.

9.2.4 Study Endpoints

9.2.4.1 Primary Endpoint The difference in the proportion of induced Treg cells (CD45RA- CD25++ FoxP3++ of CD4+ T cells) from baseline to the end of maintenance therapy.

9.2.4.1.1 Clinical outcomes will be defined as follows:

- Treatment Failure: Failure to achieve the minimum maintenance dose (600 mg) of peanut protein by 12 months, or an ED <1443 mg at DBPCFC2, or ED at DBPCFC3 <430 mg OR <10-fold more than at DBPCFC1.
- Partial Tolerance: ED at DBPCFC3 <4430 mg but ≥430 mg AND >10-fold more than at DBPCFC1.
- Tolerance: Ingestion of 4430 mg of peanut protein at DBPCFC3 without symptoms.

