3.1 Study Endpoints

3.1.1 Primary Endpoint(s)

The difference in the proportion of induced Treg cells (CD45RA- CD25++ FoxP3++ of CD4+ T cells) from baseline to the end of maintenance therapy.

CONFIDENTIAL

Clinical outcomes will be defined as follows:

- Treatment Failure: Failure to achieve the minimum maintenance dose (600 mg) of peanut protein by 12 months, or an ED <1443 mg at DBPCFC2, or ED at DBPCFC3 <443 mg OR <10-fold more than at DBPCFC1.
- Partial Tolerance: ED at DBPCFC3 <4430 mg but ≥430 mg AND >10-fold more than at DBPCFC1.
- Tolerance: Ingestion of 4430 mg of peanut protein at DBPCFC3 without symptoms.

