5.6 Modification or Discontinuation of Investigational Product(s) / Intervention Material(s)

5.6.1 Modification of Investigational Product(s) / Intervention(s)

Participants receiving active treatment who react to <1443 mg peanut protein during DBPCFC2 will be considered a treatment failure and be recommended to return to a strict peanut avoidance diet.

If the participant tolerates <4430 mg peanut protein during the DBPCFC3, he or she may elect to resume daily peanut protein dosing either at the highest tolerated dose during the challenge or 4000 mg peanut protein (whichever is less). If less than 4000 mg peanut protein, the daily dose will be increased by 25% every 2 weeks (\pm 4 days) as tolerated at the MGH CRC until they reach a dose of 4000 mg of peanut protein. They will continue on a dose of 4000 mg peanut protein for 1 year. At that time, they may elect to repeat a challenge.

At study end, those participants who are neither treatment failures nor achieve full tolerance, as determined by the DBPCFC3, may elect to have a nutrition consult to review a diet that would allow for the daily consumption of peanut protein at a dose that is tolerated without symptoms. The subject may also elect to resume strict avoidance. These subjects will continue to be followed at the MGH Food Allergy Center.

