7.4 Main Study Visits

7.4.1 Double-Blind Placebo-Controlled Food Challenge 1 (Day 28)

Participants will come to the MGH CRC four weeks (± 4 days) after the baseline visit for a double-blind, placebo -controlled food challenge (DBPCFC1) to peanut. In a DBPCFC, two challenges, one containing placebo material (toasted oat flour) and one containing peanut flour will be performed on two days within a two week period. The order of challenge will be determined by coin toss by the dietitian and will be unknown to the study nurse, investigator, and study participant. The MGH CRC dietician will prepare the challenge materials. Details of the DBPCFC procedure are below in section 7.7.1.

Prior to each challenge, the participant will have a physical exam with vital signs, spirometry, and an IV will be placed. A negative urine pregnancy test will be documented for female participants of child-bearing potential; if the test is positive, the visit will be cancelled and if pregnancy is confirmed, the subject will be withdrawn from the study. The participant will be required to have a baseline FVC and FEV1 >80% of their predicted values and an FEV1/FVC of >0.7 or the DBPCFC will be rescheduled. A study nurse who is blinded to the testing material will administer the challenge. The supervising physician will be present during the challenge and will also be blinded to testing material.

A member of the study staff will follow up with participant with a telephone call the day after the DBPCFC for active safety monitoring.

If the participant reacts at the 300 mg dose of peanut protein or less (443 mg cumulative), he/she will be randomized to receive active or placebo OIT.

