7.7 Study Procedures

7.7.1 Double-Blind Placebo-Controlled Food Challenge

In a DBPCFC, two challenges, one containing placebo oat flour and one containing peanut flour, will be performed. The dietitian will perform the preparation of the challenge materials. Prior to the food challenge, participants will be asked to restrict the use of antihistamines (short-acting, 72 hours: long-acting, 7 days), beta-agonists (12 hours), theophylline (12 hours), and cromolyn (12 hours). For DBPCFC1, one challenge will consist of 5 doses of peanut powder given every 20 minutes in increasing amounts up to a cumulative total of 443 mg of peanut protein masked by inclusion in vehicle food. Available vehicle foods will include rice milk, soymilk, mint chocolate mousse, or applesauce. The other challenge will consist of oat flour given also in 5 doses in an identical volume of vehicle food. For the active challenge, the first ingested dose will be 3 mg, then increasing to 10 mg, 30 mg, 100 mg, and 300 mg of peanut protein[?]. The placebo challenge doses will be the equivalent amount of oat flour by weight.

The protocol of the DBPCFC2 will be identical to DBPCFC1, but with additional doses of 1000 mg and 3000 mg for a cumulative dose of 4443 mg peanut protein. DBPCFC3 will follow a slightly different schedule of doses: 30 mg, 100 mg, 300 mg, 1000 mg, and 3000 mg for a cumulative dose of 4430 mg peanut protein.

If the participant has a subjective reaction to one of the doses, the study nurse may repeat that dose or consult with the supervising physician. If symptoms do not recur, the study nurse will continue the DBPCFC protocol after confirming with the supervising physician. If the study nurse is unsure about how to proceed, the supervising physician will be consulted to determine the appropriate action. Food challenges will be immediately stopped and the participant promptly treated for objective signs and symptoms as indicated in Figure 15.4, consistent with the 2010 NIAID-sponsored expert guidelines for the diagnosis and management of food allergies [?].

After the final dose of each challenge or the resolution of any suspected reaction symptoms, the participant will be observed for a minimum of 2 additional hours.

All food challenges will be performed under direct physician supervision. The supervising physician may stop a challenge if he/she feels it is in the best interest of the participant. Incomplete or indeterminate challenges will be rescheduled.

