9 SAMPLE SIZE CALCULATIONS AND STATISTICAL PLAN

9.1 Sample Size and Power Calculations

As the hypothesis regarding Treg induction and clonal tolerance can only be defined among those individuals who achieve desensitization and go on to DBPCFC3, the analysis will be per protocol for those participants who complete both post treatment challenges. The difference in the proportion of Treg will be compared between the groups using Students t test for comparison of means. Because we are expecting the primary outcome variable (difference in the proportion of Treg) to be log-normally distributed, we plan to carry out the t test on the log transformed variable. We will be powered at the expected effect on Treg if as few as six individuals (20% clinical effect and 10% dropout) who complete the protocol achieve our defined measure of at least partial clinical tolerance. Table 15.6 shows power calculations around these assumptions using a two sided t test at an alpha level of 0.05.

The sample size selected is 30 active treatment and 10 placebo treatment. We are applying the following assumptions for our power analysis (see Figure 15.5 for schema of assumptions).

- Approximately 27% of the Active Treatment group (8/30) will achieve Partial Tolerance (ED at DBPCFC3 <4430 mg but ≥430 mg AND >10-fold more than at DBPCFC1) or Full Tolerance (no reaction at DBPCFC3).
- The comparison of interest is between the combined Tolerance/Partial Tolerance and Active Treatment Failure groups who complete DBPCFC3.
- Those who fail to become desensitized after active treatment and those who receive placebo treatment are not fully informative for the primary endpoint and are therefore excluded for the per protocol analysis.
- The difference from baseline to the end of maintenance therapy in the mean proportion of induced Treg (CD45RA- CD25++ FoxP3++ of CD4+ T cells) between the Tolerance/Partial Tolerance and Treatment Failure groups will be 1.5 times the standard deviation.

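### Treatment Failure is below 443 mg in 3.1.1 but below 430 mg in 9.2.4.1.1, and a rise of exactly 10-fold that clears the mg cut-off has no group, so the two samples of the primary t test are not fully defined

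*Combined protocol and SAP*

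**What the plan says.** Section 9.1 names the primary contrast: "The comparison of interest is between the combined Tolerance/Partial Tolerance and Active Treatment Failure groups who complete DBPCFC3". Three clinical outcome groups feed it, and they are defined twice.

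- Treatment Failure in 3.1.1 ends with "or ED at DBPCFC3 <443 mg OR <10-fold more than at DBPCFC1".
- Treatment Failure in 9.2.4.1.1 ends with "or ED at DBPCFC3 <430 mg OR <10-fold more than at DBPCFC1".
- Partial Tolerance is worded the same way in 3.1.1, 9.1 and 9.2.4.1.1: "ED at DBPCFC3 <4430 mg but ≥430 mg AND >10-fold more than at DBPCFC1".
- Tolerance, in both endpoint sections, requires 4430 mg at DBPCFC3 with no symptoms.

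Failure can also arise earlier, from not reaching 600 mg or from an ED below 1443 mg at DBPCFC2. What follows concerns participants who have cleared both of those criteria.

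Section 7.7.1 gives the dose ladders. At DBPCFC1, "the first ingested dose will be 3 mg, then increasing to 10 mg, 30 mg, 100 mg, and 300 mg of peanut protein". At DBPCFC3, "30 mg, 100 mg, 300 mg, 1000 mg, and 3000 mg for a cumulative dose of 4430 mg peanut protein". Section 9.2.2 puts every active participant who completes DBPCFC3 in the per-protocol sample.

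**The concern.** A two-sample test needs each analysed participant to be in exactly one sample. Here 3.1.1 contradicts 9.2.4.1.1, and it also contradicts itself: an ED of 430 mg with more than a 10-fold rise is both Failure and Partial Tolerance. In both sections Failure needs less than 10-fold and Partial Tolerance needs more than 10-fold, so equality is in neither. A participant in that gap belongs to the per-protocol set but to neither arm of the comparison, and no rule says whether to assign or drop that person.

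The timing adds to the problem. Under 7.4.4 and the schedule in 16.1, the end-of-maintenance T cell sample is taken before DBPCFC2, so both Treg measurements can exist before DBPCFC3 fixes the group. The documents do not say whether groups are assigned before Treg results are known. Several mechanistic secondary endpoints in 3.1.2 (TCR diversity, skin test, basophil, IgG4, gene expression) use the same groups.

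**Working it through.** **Scale of ED.** The plan has no one-line definition. I take ED as the cumulative dose at the reacting step, because the cut-offs 430, 443, 1443 and 4430 mg are all running totals of the challenge ladders. Section 7.4.1 also states its threshold that way: "If the participant reacts at the 300 mg dose of peanut protein or less (443 mg cumulative". Section 5.6.1 treats 1443 mg as a reacting dose: "Participants receiving active treatment who react to <1443 mg peanut protein during DBPCFC2 will be considered a treatment failure".

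**Cumulative steps from 7.7.1.**

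- DBPCFC1: 3; 3+10 = 13; 13+30 = 43; 43+100 = 143; 143+300 = 443 mg.
- DBPCFC3: 30; 30+100 = 130; 130+300 = 430; 430+1000 = 1430; 1430+3000 = 4430 mg.
- Step-by-step ratios: 30/3 = 130/13 = 430/43 = 1430/143 = 4430/443 = 10.

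A tie at exactly 10-fold is therefore built into the schedules.

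**Applying the definitions literally to all 5 × 5 = 25 reacting pairs.** The cells at issue are:

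| DBPCFC1 → DBPCFC3 (mg) | Ratio | Under 3.1.1 | Under 9.2.4.1.1 |
|---|---|---|---|
| 3 → 430 | 143.3 | Failure and Partial | Partial |
| 13 → 430 | 33.1 | Failure and Partial | Partial |
| 43 → 430 | 10 | Failure | none |
| 143 → 1430 | 10 | none | none |
| 443 → 4430 | 10 | none | none |
| 3, 13, 43 or 143 → 4430 | above 10 | none | none |

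The other two ties, 3 → 30 and 13 → 130, are Failure in both sections because they fall below either mg cut-off. The last row has no group because 4430 mg is not below 4430 mg and a reaction is not symptom-free.

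- 9.2.4.1.1: 13 Failure + 5 Partial + 7 unplaced = 25.
- 3.1.1: 14 Failure + 3 Partial + 2 in both + 6 unplaced = 25.

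The four pairs in the last row are in doubt only between Partial Tolerance and Tolerance, which the primary test combines, provided nobody drops them. Setting them aside leaves failed-versus-tolerant placement open in 7 − 4 = 3 pairs under 9.2.4.1.1 and (6 − 4) + 2 = 4 pairs under 3.1.1. The sections disagree on three: 3, 13 and 43 → 430.

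**If ED were the single reacting dose.** No step lies between 430 and 443 mg, so the conflict between sections moves nobody. The last step is 3000 mg, so the final-step gap closes. The ties 100 → 1000 and 300 → 3000 remain unplaced in both sections.

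**Power, for illustration.** Two-sided t test, α = 0.05, df = n1 + n2 − 2, noncentrality = d/√(1/n1 + 1/n2). For 8 v 14 and d = 1.5: 1.5/√(1/8 + 1/14) = 3.38 on 20 df, giving power 0.896. Table 15.6 states 0.90, so the plan's figure reproduces.

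| Change from 8 v 14 | One participant | Two participants |
|---|---|---|
| Tolerant dropped | 0.867 (7 v 14) | 0.828 (6 v 14) |
| Failure dropped | 0.886 (8 v 13) | 0.874 (8 v 12) |
| Tolerant counted as Failure | about 0.80 | about 0.68 |
| Failure counted as tolerant | about 0.81 | about 0.70 |

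The last two rows are simulated with normal data, a true 8 v 14 and a pooled t test. One or two affected participants is my assumption.

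**The case against.** The best counter-argument comes from the primary objective in 2.1, which contrasts those who reach significant tolerance with those who do not and labels the latter Treatment Failure. Section 9.1 also counts failures as the remainder (8 + 14 = 22). Treating Failure as everyone who is not Tolerance or Partial Tolerance would put 43 → 430, 143 → 1430 and 443 → 4430 in Failure, and 3 → 430 and 13 → 430 in Partial Tolerance. The 443 mg figure could then be dismissed as carried over from DBPCFC1, since it is not a DBPCFC3 step.

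That reading is reasonable, but the plan does not state it as a rule. Section 2.1 refers forward to the definitions, and Failure has its own explicit and conflicting ones. Read literally, a residual rule would also put every last-step reaction in Failure, including rises well above 10-fold. Changing 443 to 430 still leaves the three ties without a group. The wording in 2.2.1 that counts 10-fold or more as success concerns desensitization at DBPCFC2 and does not settle the matter.

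Several limits do stand. The conflict at 430 mg and the last-step gap depend on a cumulative ED. Section 7.7.1 allows a dose to be repeated after a subjective reaction, which moves cumulative totals off the listed steps. Challenges are blinded to material, so only the boundary rule is open, not the ED itself. The misplacement figures presume a known true group and give a boundary participant the full 1.5 SD difference; they show how sensitive a small test is and do not measure this defect.

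**Conclusion.** The point holds and should be settled before analysis. The definitions that form the two samples of the primary test conflict between sections, overlap within 3.1.1 and are not exhaustive. The tie at exactly 10-fold is present on either scale of ED; the remaining faults require the cumulative reading, which the cut-offs support.

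The number of participants affected is unknown. Pair counts are not probabilities, and the plan gives no expected distribution of ED at DBPCFC3. Section 1.6.1 cites a median baseline ED of about 45 mg (interquartile range 4.5 to 200 mg) from another study, without saying whether it is cumulative. That range contains the 13, 43 and 143 mg steps, so the baseline values at issue are not remote. With 8 expected in the smaller group, even one placement matters. The power arithmetic in Table 15.6 is sound and is not in question.

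**What to change.** Reconcile 3.1.1, 9.1 and 9.2.4.1.1 into one mutually exclusive and exhaustive set of definitions:

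- define ED in one line, including whether it is cumulative and how repeated doses count;
- state the same mg cut-off for Failure and Partial Tolerance wherever they appear;
- assign exactly 10-fold to one side;
- assign a reaction at the last DBPCFC3 step to a group.

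The choice of values is the sponsor's. Section 9.4 requires an amendment for changes to principal features. It should be final before those assigning groups see any Treg result, and the plan should say so. The cost is wording in two endpoint sections and one bullet of 9.1, with no extra data or visits.

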4 SELECTION AND WITHDRAWAL OF PARTICIPANTS

4.1 Inclusion Criteria

Individuals who meet all of the following criteria are eligible for enrollment as study participants:

- Diagnosis of peanut allergy by medical history
- Evidence of peanut-specific IgE by either: positive skin prick test to peanut (reaction wheal at least 5 mm larger than saline control) or serum peanut-specific IgE ≥5 kU/L at screening visit.
- Ara h 2 specific IgE >0.35 kU/L at screening visit.
- Who are willing to sign informed consent or whose parent or legal guardian is willing to sign the consent form (age appropriate)
- Who are willing to sign the assent form, if age appropriate
- Males and females of all ethnic/racial groups aged 7-55 years old who are otherwise healthy.
- React to ≤443 mg of peanut protein during DBPCFC1

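### If ED is cumulative, a first reaction at the last DBPCFC3 step belongs to no outcome group; and entrants with a baseline ED of 443 mg can never be Partial Tolerance

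*Combined protocol and SAP*

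**What the plan says.** Section 7.7.1 sets the challenge doses. At DBPCFC1 "the first ingested dose will be 3 mg, then increasing to 10 mg, 30 mg, 100 mg, and 300 mg of peanut protein"; at DBPCFC3 the steps are "30 mg, 100 mg, 300 mg, 1000 mg, and 3000 mg for a cumulative dose of 4430 mg peanut protein". Section 4.1 admits participants who "React to ≤443 mg of peanut protein during DBPCFC1". Section 7.4.1 ties that limit to the cumulative scale: "If the participant reacts at the 300 mg dose of peanut protein or less (443 mg cumulative".

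Sections 3.1.1 and 9.2.4.1.1 define three clinical outcomes, and 9.1 repeats the Partial and Full Tolerance definitions:

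- Partial Tolerance: "ED at DBPCFC3 <4430 mg but ≥430 mg AND >10-fold more than at DBPCFC1", the same in all three places.
- Tolerance: "Ingestion of 4430 mg of peanut protein at DBPCFC3 without symptoms"; in 9.1, "Full Tolerance (no reaction at DBPCFC3".
- Treatment Failure at DBPCFC3, in 9.2.4.1.1: "ED at DBPCFC3 <430 mg OR <10-fold more than at DBPCFC1". Section 3.1.1 has 443 mg in place of 430 mg.

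Section 9.2.2 puts every active participant who completes DBPCFC3 in the per-protocol sample. Section 9.1 compares the change in Treg between the combined Tolerance/Partial Tolerance group and the Treatment Failure group in that sample.

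**The concern.** A participant who tolerates 1430 mg cumulative and reacts only at the last DBPCFC3 step has the second-best result the challenge can give. On the cumulative reading of ED, the strict upper cap keeps that result out of Partial Tolerance, and the reaction keeps it out of Tolerance. It is not Failure at DBPCFC3 either, since the ED is above the floor and at least 10-fold the baseline value. The participant is therefore in the per-protocol sample but in neither arm of the primary t test.

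The top DBPCFC3 total is also exactly 10 times the entry limit, and Partial Tolerance requires more than 10-fold. The least sensitive entrants allowed in therefore have no route to Partial Tolerance.

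These rules form the two groups of the primary comparison, and one of them is expected to hold only 8 people. Where the rules give no answer, someone has to choose a group case by case after DBPCFC3.

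**Working it through.** **Possible EDs (cumulative, including the reacting dose).**

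- DBPCFC1: 3; 3+10 = 13; 13+30 = 43; 43+100 = 143; 143+300 = 443 mg.
- DBPCFC3: 30; 30+100 = 130; 130+300 = 430; 430+1000 = 1430; 1430+3000 = 4430 mg; or no reaction.

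**Every pair against the 9.2.4.1.1 rules** (F Failure, PT Partial Tolerance, T Tolerance, – no group):

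| ED at DBPCFC1 | 30 | 130 | 430 | 1430 | 4430 | no reaction |
|---|---|---|---|---|---|---|
| 3 | F | F | PT | PT | – | T |
| 13 | F | F | PT | PT | – | T |
| 43 | F | F | – | PT | – | T |
| 143 | F | F | F | – | – | T |
| 443 | F | F | F | F | – | T |

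Seven of 30 cells have no group. Five are the last step, where the ratios are 4430/3 = 1477, 4430/13 = 341, 4430/43 = 103, 4430/143 = 31 and 4430/443 = 10. The other two are exact 10-fold ties, 430/43 and 1430/143, which are neither above nor below 10-fold.

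For a baseline ED of 443 mg, Partial Tolerance needs an ED above 10 × 443 = 4430 mg and below 4430 mg. No value satisfies both.

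**Other readings of ED.**

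- *Single reacting dose.* The last step is 3000 mg, under the cap, so it is PT for the four lower baseline steps. For entrants who reacted at the 300 mg dose, 3000/300 = 10, so they cannot be PT.
- *Cumulative tolerated dose.* The last step is 1430 mg, and again PT for the four lower baseline steps. For the same entrants, 1430/143 = 10, so they cannot be PT.

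The last-step gap across all baselines thus depends on the cumulative reading. The block on the least sensitive entrants does not.

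**Section 3.1.1.** With Failure set at below 443 mg, an ED of 430 mg after a baseline of 3 or 13 mg is already both Failure and Partial Tolerance. If only the fold rule became inclusive, a baseline of 43 mg would join them.

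**Power.** Two-sided t test, α = 0.05, noncentrality = d·√(n₁n₂/(n₁+n₂)), df = n₁+n₂−2, d = 1.5. The plan's own case first: 8 v 14 gives 1.5·√(112/22) = 3.38 on 20 df and power 0.896, matching the 0.90 in table 15.6.

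The documents give no count of last-step reactors. Assuming 1 or 2:

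| Where they would have been | 1 reactor | 2 reactors |
|---|---|---|
| Among the 8, left out | 7 v 14: 0.87 | 6 v 14: 0.83 |
| Among the 14, left out | 8 v 13: 0.89 | 8 v 12: 0.87 |
| True responders filed as Failure | 7 v 15: 0.80 | 6 v 16: 0.68 |

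The last row is simulated, because responders in the Failure group also dilute its mean: the expected difference drops to 1.5 × 14/15 = 1.40 SD with one and 1.5 × 14/16 = 1.31 SD with two.

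**Share of entrants at 443 mg.** Section 1.6.1 cites a median ED of 45 mg and an interquartile range of 4.5 to 200 mg for the oldest group of a paediatric study. Assuming log-normality, the SD on the log scale is (ln 200 − ln 4.5)/1.349 = 2.81. Then P(ED ≤ 143) = 0.659 and P(ED ≤ 443) = 0.792, so the share of eligible entrants at the top step is (0.792 − 0.659)/0.792 = 0.17.

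**The case against.** ED is never formally defined, and on two other readings a last-step reaction is Partial Tolerance for most entrants. That stands, so this limb must be stated as conditional. The cumulative reading is still the natural one: 443, 1443, 430 and 4430 are all cumulative sums, and 7.4.1 equates a reaction at the 300 mg dose with 443 mg cumulative.

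The intended grouping can also be guessed. Section 5.6.1 speaks of participants who are neither failures nor fully tolerant as a middle group, which is where a last-step reactor would naturally go. That makes the strict cap look like a slip, but 5.6.1 concerns options after the study and does not amend the analysis definitions.

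A reader might infer that these participants become Failures and that power drops to 0.68. The documents do not support this: the written rule does not make them Failures, and the figure further assumes two of them, each with the full responder effect. Nor is it certain that they come out of the 8. Section 9.1 defines the 8 using the same cap, so on the cumulative reading they may lie outside it, and the loss is then only to 0.89 or 0.87. The plan itself accepts as few as six in the tolerance group, with power 0.82 for 6 v 13.

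Finally, demanding a large gain from every entrant is a legitimate design choice. But the plan nowhere says that it means to deny Partial Tolerance to the least sensitive people it admits.

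**Conclusion.** The definitions are wrong as written, on two limbs of different strength.

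- If ED is cumulative including the reacting dose, a first reaction at the last DBPCFC3 step has no group, whatever the baseline ED.
- Entrants with a baseline ED of 443 mg cannot be Partial Tolerance on any of the three readings examined. A reader might infer that they cannot succeed at all; that goes too far, since Tolerance remains open to them.

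The likely cost in power is small to moderate: from 0.90 to between 0.83 and 0.89 if 1 or 2 participants are left out, with 0.80 or 0.68 as a worst case that the rules do not prescribe. The count of 1 or 2 is an assumption.

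The 17% is the estimated share entering at 443 mg, not the share reacting at the last step. It rests on log-normality and on a study of children aged 3 to 18, whereas this trial enrols ages 7 to 55.

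The stronger reason to act is that membership of the primary comparison groups is left open for a reachable result in a very small sample.

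**What to change.** For the analysis definitions only:

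1. State that ED is the cumulative dose including the dose that provoked the reaction.
2. In 3.1.1, 9.1 and 9.2.4.1.1, define Partial Tolerance as a reaction at DBPCFC3 with ED at least 430 mg and at most 4430 mg, and at least 10-fold the DBPCFC1 ED. Both inequalities must change. The cap alone leaves 443 mg entrants and the two exact ties without a group; the fold rule alone leaves all five last-step results without one.
3. Reconcile the Failure cut-off in 3.1.1 (below 443 mg) with 9.2.4.1.1 (below 430 mg), so that Failure ends where Partial Tolerance begins.

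With the 9.2.4.1.1 cut-off, steps 1 and 2 put each of the 30 result pairs in exactly one group. The cost is one sentence and two inequalities in three places, plus one reconciled figure, made by protocol amendment as 9.4 requires. No new data are needed, and no challenge dose or participant management changes.
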